1.10 Timetable/Schedule of Events

[figure not shown]
The project will be conducted over a 2-year period (See Table below). Start-up activities took ~ 1 month. Aim 1 data collection is complete. Dissemination is ongoing with an abstract accepted for presentation at Academy Health in June 2021, a manuscript under review *at JAMA Open Network* and 3 other manuscripts in development. Aim 2 will be completed by Month 18. Final data analyses, preparation of manuscripts, and final dissemination materials will be completed by Month 24.

MILESTONES AND ACTIVITIES	2020				2021								2022													
	S	O	N	D	J	F	M	A	M	J	J	A	S	O	N	D	J	F	M	A	M	J	J	A		
IRB approvals and revisions	X	X	X	X	X	X	X	X	X	X	X	X	X	X	X	X	X	X	X	X	X	X	X	X	X	
Convene Scientific and Community Advisory Groups	X	X	X	X	X	X	X	X	X	X	X	X	X	X	X	X	X	X	X	X	X	X	X	X	X	
Convene Design Teams	X	X	X	X	X	X	X	X	X	X	X	X	X	X	X	X	X	X	X	X	X	X	X	X	X	
Participate in monthly CDCC cross site meetings/workgroups	X	X	X	X	X	X	X	X	X	X	X	X	X	X	X	X	X	X	X	X	X	X	X	X	X	
Aim 1:																										
Convene Virtual Community Conversations	X	X	X																							
Convene Community Engagement Virtual Salons			X	X	X																					
Conduct rolling qualitative analyses	X	X	X	X	X	X																				
Summarize results and prioritization of messages and strategies	X	X	X	X	X	X																				
Co-design of intervention messaging and materials			X	X	X	X																				
Finalize intervention materials with SmithGifford						X	X																			
Progress reports to CDCC (i.e., barriers and facilitators of COVID-19 testing)	X	X	X	X	X	X																				
Aim 2:																										
HCW and CBO intervention arms						X	X	X	X	X	X	X	X	X	X	X	X	X								
-Intervention activities						X	X	X	X	X	X	X	X	X	X	X	X	X								
-COVID-19 testing and participant data collection						X	X	X	X	X	X	X	X	X	X	X	X	X								
Cost analyses						X	X	X	X	X	X	X	X	X	X	X	X	X								
Process evaluation						X	X	X	X	X	X	X	X	X	X	X	X	X								
-Key informant interviews								X	X	X	X	X	X	X	X	X	X	X								
Progress reports to CDCC (i.e., testing results, barriers and facilitators of COVID-19 testing)						X	X	X	X	X	X	X	X	X	X	X	X	X								
Analysis and Dissemination																										
Manuscript preparation and dissemination						X	X	X	X	X	X	X	X	X	X	X	X	X								

2.2 Research Staff Training

Staff are CITI trained and receive continuous training and professional development in the conduct of human subjects research. Weekly project administration meetings focused on data collection, quality and management are employed.

2.3 Resources Available

A. Facilities

This research is supported by a multi-disciplinary collaboration of faculty from the NJ Alliance for Clinical and Translational Science (NJ ACTS) inclusive of Robert Wood Johnson Medical School, Rutgers School of Public Health, Center for Advanced Biotechnology and Medicine and the Rutgers Office of University-Community Partnerships. NJ ACTS is funded by the National Center for Advancing Translational Sciences (NCATS), an institute of the National Institutes of Health (NIH). The NJ ACTS CTSA is designed to provide infrastructure and resources to promote and foster an institution's capacity for conducting clinical and translational research. The overall goal of the CTSA program is transform the translational science process in an effort to speed the delivery of new drugs, diagnostics and medical devices to patients and to use those research discoveries to change public policy, impact healthcare delivery and improve population health. NJ ACTS provides infrastructure for our faculty and staff as well as quantitative data collection/management (e.g., automated survey data collection using Redcap) and qualitative data collection (e.g., depth interviews, field observations, participant observation, focus groups) and management using ATLAS.ti software.

2.4 Research Sites

Rutgers Biomedical and Health Sciences is the research site for this study. Rutgers staff will conduct all research activities.

While we are working with Vault Health, Inc. to collect study specimens and Parker Health, the Visiting Nurse Association, University Hospital and Robert Wood Johnson University Hospital and 18 community based organizations to inform potential participants about the availability of the research, their engagement in the project does not meet the definition of engaged in human subjects research under items #1 (Vault) and #4 of the section entitled: ***Institutions Not Engaged in Human Subjects Research:***

<https://www.hhs.gov/ohrp/regulations-and-policy/guidance/guidance-on-engagement-of-institutions/index.html>

Vault Health meets the criteria of non-engagement under stipulation #1: It is an organization whose employees perform commercial services for investigators (i.e., COVID testing) and their services for this project: (1) do not merit professional recognition or publication privileges; (2) their COVID testing services are typically performed for non-research purposes for the NJ Department of Health and direct to consumers; and, (3) the outreach materials and strategies in this protocol are the intervention not the COVID test; therefore, Vault's employees or agents do not administer any study intervention being tested or evaluated under the protocol.

Similarly, the healthcare and community based organizations meet the criteria of non-engagement under stipulation #4: These organizations employees or agents will only be engaged in: (1) informing prospective subjects about the availability of the research; (2) providing prospective subjects with information about the research (which may include a copy of the relevant informed consent document and other IRB approved materials) but do not obtain subjects' consent for the research or act as representatives of the investigators; (3) providing prospective subjects with information about contacting investigators for information or enrollment; and/or (4) seeking or obtaining prospective subjects' permission for investigators to contact them.

3.0 Multi-Center Research

This project is funded by the NIH RADxUP program and is coordinating data collection with the RADxUP Coordination and Data Collection Center at Duke University. A draft of the data use agreement which is in final signature process and awaiting approval of the Aim 2 consent form by the Rutgers IRB has been included as an attachment.

4.0 Subject Considerations

4.1 Subject Selection and Enrollment Considerations

A. Method to Identify Potential Subjects

We will work with 18 community based organizations, Parker Health, the Visiting Nurse Association, University Hospital Newark and Robert Wood Johnson University Hospital to develop strategies to identify and engage potential research participants. To ensure that the NJ HEROES TOO intervention is relevant to healthcare worker families and their communities, we will engage them and their advocates in a co-design process. Based on the results of this process in Aim 1, we will widely implement recruitment strategies engaging low income HCWs as ambassadors to recruit their families/contacts into the NJ HEROES TOO arm as well as general community members through the traditional arm of the study.

B. Recruitment Details

Recruitment of Aim 1 participants. The purpose of Aim 1 is to Co-design and develop innovative, user centered outreach intervention strategies that will then be used in Aim 2. To recruit participants for the virtual community conversations and key informant interviews that will inform Aim 1, we will use snowball sampling methods, as we have done in previous studies, drawing on confirmed participants to identify additional potential participants who will serve confirming and disconfirming roles. As needed, we will work with our collaborating healthcare institutions and community-based organizations to identify potential participants. They will advertise the virtual community conversation opportunity through their preferred standard community outreach channels (e.g. posted flyers (see recruitment flyers), mailings with flyers enclosed and announcements at community events using language from the flyers) as well as through additional multimedia approaches such as attaching the flyers to emails sent to list serves. Interested individuals will initiate contact with the Rutgers study team via email or phone using information included in the flyer. A Rutgers research staff member will screen participants for eligibility. Aim 1 participants will be Black and Latinx individuals who are knowledgeable and able to speak about their experiences and the factors that are important and impact COVID testing from diverse perspectives. We will convene 8-10 community focus group conversations, consisting of 10-12 ethnically homogenous participants each, representing Black and Latinx stakeholders. We will also recruit 15-20 HCW for key informant interviews. The literature suggests that for our purposes, 2-3 groups per strata and 6-10 interviews are sufficient to reach full saturation. We will offer a \$30 gift card incentive to all participants.

Recruitment of NJ HEROES TOO arm (Aim 2). In this arm of study aim 2, we will recruit low income health care workers (HCW) employed at several NJ healthcare centers in affected counties to be “ambassadors” to help extend recruitment to their family members and community contacts. We will do so through our two current HCW cohorts, the Rutgers Corona Cohort (RCC) and the Robert Wood Johnson Screening Study (RWJSS) (total Black and Latinx n~1300) which have recruited participants at University Hospital and Robert Wood Johnson University Hospital. Additionally, to increase the reach of our HCW intervention beyond academic medical and healthcare system settings, we have partnered with Parker Health (representing nursing home and assisted living facility HCWs) based in Middlesex county and the Visiting Nurse Association Health Group (VNA), which is a statewide home healthcare organization with significant activities in Essex, Union and Passaic counties. Specifically, the organizations will: (1) inform prospective subjects about the availability of the research (e.g.,

announce the study at meetings with their staff, post links to the study website on their website, on their list serves, in their newsletters and social media); (2) provide prospective subjects with information about the research (i.e., share recruitment materials with their staff); (3) provide prospective subjects from their staff with information about contacting investigators for information or enrollment; and/or (4) ask their staff permission for investigators to contact them.

These approaches leverage trusted relationships (with the HCW), use culturally and linguistically responsive materials, and reduce the burden of testing by using mailed saliva kits to address common barriers encountered by the targeted populations. Campaign materials will also include lists of community resources that can provide support in the event of positive test result, since the potential effects of a positive result and quarantine on employment and a person's ability to meet basic needs are themselves significant barriers. Where applicable (such as in our ongoing cohorts), we will send e-mail blasts/flyers, and place posters and informational kiosks in key hospital and clinical locations. Recruitment materials in English have been developed are part of this protocol amendment. Once they have been approved we will submit Spanish translations for IRB for approval prior to their use.

Electronic survey data collection: Interested individuals can click active hyperlinks, scan QR codes or type in URLs from recruitment materials to obtain more information on the study and assess their eligibility. Informed consent will be collected electronically after which consented individuals will complete demographic questionnaires about themselves and their households. They will then be asked to extend the invitation to their "spheres of influence" (household and other family members/community contacts) to reach populations who would not otherwise have access to testing. The ambassadors will receive an e-mail and/or text message with an URL link to forward to their contacts. By clicking that link, the household and other family member/community contact will be taken to a webpage with information on NJ HEROES TOO testing, including contact information for study staff.

Telephone data collection: For individuals who are not able to enter their own information electronically, a phone number will be provided for the study. They can use it to reach a research staff member who will consent them, administer the survey by phone and set them up with Vault Health for testing.

Recruitment of the community-based comparison group arm (Aim 2). For the traditional, community based arm of study aim 2, recruitment will be channeled through extant community-based organizations focused on underserved communities in the counties of interest. These partner organizations will advertise the testing opportunity through their preferred standard community outreach channels (e.g. mailings, flyers, community events) as well as through additional multimedia approaches identified and developed during Aim 1. As in the NJ HEROES TOO arm, interested individuals can either opt for electronic or telephone data collection.

C. Subject Screening

▪ Eligibility Criteria

Aim 1: (1) self-identification as Black or Latinx; (2) age 18 or older; and, (3) have access to phone, internet and/or email/text messages; and, (4) ability to speak, understand, and/or read English or Spanish.

Aim 2 Healthcare Workers: (1) self-identification as Black or Latinx; (2) employment at one of the participating health care settings (Parker Health, Robert Wood Johnson University Hospital, University Hospital, Visiting Nurse Association); (3) resident of Union, Passaic, Middlesex, or Essex County, NJ; and, (4) age 18 or older..

Aim 2 Healthcare Worker household members/contacts: (1) self-identification as Black or Latinx; (2) resident of Union, Passaic, Middlesex, or Essex County, NJ; (3) age 4 or above; (4) able to provide informed consent/assent; and (5) ability to speak, understand, and/or read English or Spanish.

Aim 2 Community members: (1) residence in the counties of interest (Union, Passaic, Middlesex, or Essex County, NJ); (2) self-identification as Black or Latinx; (3) age 18 or older; (4) ability to speak, understand, and read English or Spanish; and, (5) ability to provide informed consent.

Aim 2 Community household members/contacts: 1) self-identification as Black or Latinx; (2) resident of Union, Passaic, Middlesex, or Essex County, NJ; (3) age 4 or above; and (4) able to provide informed consent/assent; and (5) ability to speak, understand, and/or read English or Spanish.

Aim 2 Children: (1) Age 4 or above; (2) Parent/ legal guardian able to provide permission to participate

4.2 Secondary Subjects

N/A

4.3 Number of Subjects

A. Total Number of Subjects

We anticipate a total of 3000 participants will be enrolled across the two study aims.

Aim 1: We recruited 13 groups and 8 individual interviews with stakeholders who identified as Black and/or Latinx (n=111 individuals).

Aim 2: The goal is to enroll approximately 1000 participants in each of the two study arms (N=2000) over a 12 month period.

We are experiencing a high loss to follow-up rate in Aim 2. Though interest, consent rates and survey completion are high there is also a high rate of loss to follow-up. COVID-19 testing is the study outcome and uptake among participants is low. Therefore, we may need to enroll more than 1000 per arm.

B. Total Number of Subjects If Multicenter Study

N/A

C. Feasibility

For Aim 1 and Aim 2 community based organization arm, drawing from long-established relationships and community partners of MPIs [name], [name], and [name] we have engaged 18 community organizations in the design and development of this project. Organizations serve the cities of Newark, Elizabeth, Irvington, Hillside, Caldwell, Paterson, New Brunswick, Perth Amboy, and their surrounding areas. They range in size, scope and focus from faith-based organizations to large social service groups.

For the Aim 2 HCW arm, our current COVID-19 surveillance cohorts include nearly 4000 HCWs, of whom we estimate 32% (n~1300) meet criteria to serve as ambassadors. We anticipate that approximately 1000 more HCWs from Parker Health and the Visiting Nurse Association will be eligible.

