1.5 Sample Size Justification

For Phase 1, Virtual Community Conversations we will convene 8-10 community focus group conversations of 10-12 ethnically homogenous participants each representing Black and Latinx stakeholders (i.e., healthcare workers, family members and community organizers). The literature suggests that for our purposes, 2-3 focus groups are sufficient to capture 80% of themes, including the most prevalent themes, and three to six groups for 90% of themes in a homogeneous study population using a semistructured discussion guide.³⁷ To reach the desired number of 15-20 healthcare workers we will supplement community conversations with individual key informant interviews with healthcare workers given they have not been able to participate in group meetings. Hennick et al suggest code saturation can be established with as few as 6 interviews with full saturation reached at nine interviews.³⁸ They determined the first interview conducted contributes more than half (53%) of new codes and three quarters (75%) of high-prevalence codes, with subsequent interviews adding a few new codes each until saturation.³⁸

Rate (expected #/month) in NJ HEROES TOO arm			
RR	80	100	120
1.15	0.78	0.82	0.81
1.2	0.94	0.96	0.95
1.3	0.99	0.99	0.99

For Phase 2, to test our Aim 2A hypothesis which compares testing uptake between the two arms power calculations are based on the primary outcome measure, testing uptake rate. We report power for rate ratios (RR; ratio of rate in comparison arm relative to intervention arm) of 1.15, 1.2, and 1.3, when expected tests per month in the intervention arm range from 80 to 120 (Table). We will have about 80% power or greater for RR of 1.15 or greater. To test hypothesis 2B, we will compare participants in the two arms on key

characteristics that may be barriers to testing (participant trust, health literacy, English proficiency and patient activation). We will do so through linear regression models, adjusting for covariates including participant age, race/ethnicity, sex, and highest level of educational attainment.

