1.6 Study Variables

In Aim 1, we will co-design, develop and implement an innovative, HCW-centric outreach intervention strategy to engage Black and Latinx minority communities. We will explore community perceptions about COVID-19 testing, treatment, and vaccination to design COVID-19 testing materials and messages that are culturally tailored to address concerns of Black and Latinx minority communities. In Aim 2, we will conduct a mixed methods study to evaluate the effectiveness and cost of: (1) the HCW-focused outreach intervention strategy versus (2) standard community engaged outreach, working with community based organizations (CBOs). We will explore contextual factors (individual, family, and community) affecting COVID-19 testing implementation outcomes and scalability. The primary outcome will be uptake of COVID-19 testing in the targeted populations.

A. Independent Variables, Interventions, or Predictor Variables

RADxUP has provided a list of common data elements that include PhenX Toolkit items with Spanish translations that will be collected across funded consortia projects. Data elements include demographics, medical history, health status, vaccine acceptance, COVID-19 testing experience and trusted information sources. We will also assess trust in healthcare using the Revised Healthcare System Distrust Scale; 9 items.

B. Dependent Variables or Outcome Measures

Our primary outcome, testing, will be measured through Vault's receipt of a saliva kit from the participant with virus test results provided directly to participants as well as to the study team.

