Quantitative: To compare participation rates in the two arms, our primary outcome, we will use data on the number of tests performed per month (over the up to 12 month study period). For each intervention, the start time is the date of first attempted contact with potential participants and the end date is either the end of the study period, or the date at which the 1000th individual was tested (whichever comes first). We assume that the number tested follows a Poisson distribution within the time period. We will test the null hypothesis that there is no difference between the two interventions, and also report a 95% confidence interval for the rate ratio. Secondly, we will examine the proportion of tested participants from vulnerable and underserved populations of interest (e.g. Black and Latinx, immigrants, children, and low-income households) in each arm through logistic regression models. We will additionally examine proportion of positive tests in the two study arms to examine whether recruitment through index HCWs taps into more highly exposed participant groups, as hypothesized. To do so we will fit logistic regression models, where the outcome is positive test results (yes/no) and the primary predictor is study arm, adjusting for covariates including participant age, race/ethnicity, sex, occupation, and highest level of educational attainment. Power calculations for this aim are based on the primary outcome measure, testing uptake rate. We report power for rate ratios (RR; ratio of rate in comparison arm relative to intervention arm) of 1.15, 1.2, and 1.3, when expected tests per month in the intervention arm range from 80 to 120 (Table X). We will have about 80% power or greater for RR of 1.15 or greater. To test hypothesis 2B, we will compare participants in the two arms on key characteristics that may be barriers to testing (participant trust, health literacy, English proficiency, and patient activation). We will do so through linear regression models, adjusting for covariates including participant age, race/ethnicity, sex, and highest level of educational attainment.

RR	80	100	120
1.15	0.78	0.82	0.81
1.2	0.94	0.96	0.95
1.3	0.99	0.99	0.99

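### The power table's 80 to 120 tests per month implies 96% to 100% uptake at the goal of about 1000 enrolled per arm; section 4.3 reports low uptake, a possible increase and 3000 in total, but no uptake figure or revised per-arm target

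*Combined protocol and SAP*

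**What the plan says.** The power table appears in sections 1.5 and 6.1. It covers RR 1.15, 1.2 and 1.3 "when expected tests per month in the intervention arm range from 80 to 120". The accompanying sentence in both sections claims roughly 80% power or more from RR 1.15 upwards. At RR 1.15 the table itself shows 0.78, 0.82 and 0.81.

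The outcome is a completed test. Section 1.6 measures it through "receipt of a saliva kit from the participant with virus test results", and section 6.1 analyses "the number of tests performed per month (over the up to 12 month study period". Each arm's counting ends when the study period ends or when its 1000th person is tested, whichever is sooner.

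Section 4.3 works in people enrolled: "The goal is to enroll approximately 1000 participants in each of the two study arms (N=2000) over a 12 month period". It then reports on progress: "We are experiencing a high loss to follow-up rate in Aim 2", and "COVID-19 testing is the study outcome and uptake among participants is low". Its response is "Therefore, we may need to enroll more than 1000 per arm". It also says "We anticipate a total of 3000 participants will be enrolled across the two study aims". Aim 1 accounts for 111 of these.

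**The concern.** The power calculation and the end rule count people tested; the recruitment goal counts people enrolled. The two coincide only if nearly everyone who enrols returns a kit, and section 4.3 says that is not happening. An arm could meet its enrolment goal while the number tested, which drives the precision of the primary rate ratio, falls below anything the table covers.

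Nothing in the plan converts a number tested into an enrolment figure, or says what power remains at the rates being achieved. The planned 95% confidence interval will show any imprecision afterwards, but it does not help the team decide now how many to enrol.

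**Working it through.** **Inputs.** Tests per month in the intervention (healthcare worker, HCW) arm: 80, 100, 120 (1.5, 6.1). Counting period: up to 12 months, ending early at 1000 tested (6.1). Enrolment goal: about 1000 per arm; total 3000; Aim 1 used 111 (4.3). One test per person, since section 1.3 describes a one-time survey followed by saliva testing. Uptake: not given.

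**Uptake implied by the table, HCW arm.**
- 80 per month: 80 × 12 = 960; 960/1000 = 96%.
- 100 per month: 1000/100 = month 10, when the end rule applies; 1000/1000 = 100%.
- 120 per month: 1000/120 = month 8.3; again 100%.

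**If the larger total is used.** 3000 − 111 = 2889 for Aim 2. The split by arm is not stated; an equal split gives about 1444 (1444.5) per arm. Then 960/1444.5 = 66% and 1000/1444.5 = 69%.

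**Reproducing the plan's power.** The test, alpha and sidedness are not stated. I assumed a Wald test on the log ratio of two Poisson rates, two-sided 0.05, 12 months in both arms, and the HCW arm faster, as in Hypothesis 2A:

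power = Φ( ln RR / √(1/n1 + 1/n2) − 1.96 ), with n1 = HCW-arm tests and n2 = n1/RR.

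At RR 1.15 and 80 per month, n1 = 960 and n2 = 835, which gives 0.84. The plan's table gives 0.78. The formula does not reproduce the table, so what follows is indicative.

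**Power with 1000 enrolled in the HCW arm.** Uptake here means HCW-arm uptake throughout, and its values are assumptions.

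| HCW-arm uptake | n1 | RR 1.15 | RR 1.2 | RR 1.3 |
|---|---|---|---|---|
| 80% | 800 | 0.77 | 0.94 | 0.998 |
| 50% | 500 | 0.57 | 0.78 | 0.97 |
| 30% | 300 | 0.38 | 0.57 | 0.85 |

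Example: RR 1.15, n1 = 500, n2 = 435; 0.1398/√(1/500 + 1/435) = 2.13; Φ(2.13 − 1.96) = 0.57.

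Sections 1.5 and 6.1 define RR as comparison over intervention, which makes the comparison arm the faster one. With n2 = n1 × RR the RR 1.15 column is 0.05 to 0.06 higher.

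**HCW-arm tests needed for 80% power.** n1 = (1 + RR) × ((1.96 + 0.8416)/ln RR)².

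| RR | n1 | Share of 1000 | Share of about 1444 |
|---|---|---|---|
| 1.15 | 864 | 86% | 60% |
| 1.2 | 519 | 52% | 36% |
| 1.3 | 262 | 26% | 18% |

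**RR detectable with 80% power**, same formula: about 1.14, 1.21, 1.28 and 1.38 at 80, 40, 25 and 15 HCW-arm tests per month.

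**The case against.** The power sentence is conditional: it holds for the rates it names. The primary outcome is a rate per calendar month, so enrolment is not its denominator. Section 4.3 calls 1000 a goal, discloses the low uptake, foresees enrolling more, and allows a total about 889 above 2000 plus 111. No analysis rule stops an arm at 1000 enrolled.

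All of this is correct. It shows that the problem is acknowledged and that the plan leaves room to respond. It does not supply an uptake figure, a per-arm target or power at lower rates, and the unqualified sentence about 80% power stays in the text beside a report that uptake is low. The 1000-tested rule is a ceiling, because an arm also ends when the study period ends.

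Three stronger readings should be resisted:
- **That the power claim itself requires 96% uptake.** That figure is what the table's lowest rate implies at 1000 enrolled. By the formula above, 80% power at RR 1.15 needs about 86% of the HCW arm, and less at larger effects or larger enrolment.
- **That the study is shown to be underpowered.** No uptake figure is given, so the documents cannot establish this. If the true RR is near 1.3, even 30% uptake leaves about 0.85.
- **That the table is wrong.** My formula does not match it, but the plan does not name its method. A Wilcoxon test on whole-month counts, with the comparison arm slower and each arm's end rule applied, comes within two points in all nine cells (0.78, 0.82 and 0.83 at RR 1.15). That match was found by trying alternatives, so it is weak evidence either way.

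**Conclusion.** The concern holds as a mismatch between people enrolled and people tested. The rates behind the power statement are not supported at the stated enrolment goal in the light of section 4.3's own report. The goal and the power sentence need to be reconciled.

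Confidence is high on the implied uptake: 96% to 100% at 1000 per arm, and 66% to 69% if 2889 were split equally. Both rest on one test per person and, at 80 per month, a full 12 months of counting. They do not depend on any power method.

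Confidence is lower on the loss of power, which rests on an assumed test, alpha and uptake. It falls mainly at RR 1.15 and 1.2, and its actual size cannot be known from the documents. This should be fixed, but it does not undermine the primary analysis.

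**What to change.** **Section 4.3.** State the per-arm target as people tested, consistent with the 1000-tested end rule, together with the uptake assumption that converts it to enrolment. For 1000 tested: 1000/0.8 = 1250, 1000/0.5 = 2000, or 1000/0.3 = 3333 enrolled per arm.

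**Sections 1.5 and 6.1.**
- Extend the power table below 80 tests per month to cover the rates being observed. Use rates pooled over arms, so that no comparative result is revealed.
- Use one stated test, alpha and direction of RR, so that the added rows are comparable with the existing ones.
- Restate the 80% power sentence for the number expected to be tested, and give the RR detectable with 80% power at that number.

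The figures in this point are a check and are not proposed as protocol text; the study statistician should produce the final ones.

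**Cost.** Some wording and an extended table. The stated power will look less favourable. No added enrolment is required, because an arm that does not reach 1000 tested still ends with the study period. The primary analysis does not change.
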